## 9.4. Interim Analysis

A 2-stage group sequential design with sample size re-estimation is used for this study. An interim analysis will be performed after 43 participants (75%) have completed the study. This interim analysis will include a binding stopping rule for efficacy if the primary endpoint (specified in Section 3) is met. Using the sample size assumptions described in Section 9.5, the

calculated O'Brien-Fleming alpha level for statistical significance on the primary endpoint is 0.00998 for the interim analysis.

If the primary endpoint does not reach the necessary significance level for early termination at the interim analysis, study enrollment will continue and the final sample size will be adaptively determined using a “promising zone” approach (Mehta, 2011). Based on the observed effect size at the interim analysis, the conditional power (ie, probability of reaching statistical significance at the final analysis given the data obtained at the interim) for the primary endpoint will be calculated. Because the Type I error probability is not inflated when using conditional power and the promising zone methodology used in this study to determine the situations in which the sample size can be increased (Mehta, 2011), no further adjustment to the O'Brien-Fleming boundaries (described in Section 9.1.1) is required for the final analysis.

The conditional power is calculated as follows (Mehta, 2011, equation 6):

$$CP = 1 - \Phi\left(\frac{z_{\alpha}\sqrt{n_2} - z_1\sqrt{n_1}}{\sqrt{\tilde{n}_2}} - \frac{z_1\sqrt{\tilde{n}_2}}{\sqrt{n_1}}\right)$$

Where:

$\Phi(\bullet)$  is the standard normal cumulative distribution function

$n_1$  = actual sample size at interim analysis (expected to be  $n_1 = 43$ )

$n_2$  = planned sample size at final analysis (ie,  $n_2 = 57$ )

$\tilde{n}_2$  = sample size increment between interim and planned final analyses (expected to be  $\tilde{n}_2 = 14$ )

$z_{\alpha}$  = the standard normal value for a type I error rate of  $\alpha$ ; ie,  $\Phi(1 - 0.025) = 1.95996$

$z_1 = \bar{x}_1 / se(\bar{x}_1)$ , the z-statistic for 24-hour SBP change from baseline computed at interim analysis

Based on the calculated conditional power, one of the following 3 actions will be taken:

1. “Favorable zone”: If conditional power  $\geq 90\%$ , continue enrolling participants until the prespecified target sample size ( $N = 57$ ).

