2. “Promising zone”: If  $40\% \leq$  conditional power  $< 90\%$ , increase the target sample size to  $(43 + \tilde{n}'_2)$ , up to a maximum of 77 completers.
3. “Unfavorable zone”: If conditional power  $< 40\%$ , continue enrolling participants until the prespecified target sample size ( $N = 57$ ).

When the conditional power falls into the “promising zone”, the additional sample size required is calculated as follows (Mehta, 2011, equation 9):

$$\tilde{n}'_2 = \left(\frac{n_1}{z_1^2}\right) \left[\frac{z_{\alpha}\sqrt{n_2} - z_1\sqrt{n_1}}{\sqrt{n_2 - n_1}} + z_{\beta}\right]^2$$

Where:

$n_1$  = actual sample size at interim analysis (expected to be  $n_1 = 43$ )

$n_2$  = planned sample size at final analysis (i.e.,  $n_2 = 57$ )

$z_{\alpha}$  = the standard normal value for a type I error rate of  $\alpha$ ; ie,  $\Phi(1 - 0.025) = 1.95996$

$z_{\beta}$  = the standard normal value for a type II error rate of  $\beta$ ; ie,  $\Phi(1 - 0.10) = 1.28155$

$z_1 = \bar{x}_1 / se(\bar{x}_1)$ , the z-statistic for 24-hour SBP change from baseline computed at interim analysis

The favorable zone threshold was set to the target study power (90%; [Mehta, 2011](#)). Based on the study parameters, the unfavorable zone threshold was determined to be approximately 40% ([Mehta, 2011](#), equations 10 to 12).

Enrollment will continue while the interim analysis is being performed. To mitigate the risk of enrolling more participants than needed (ie, “overruns”), the interim analysis will be conducted using the primary endpoint only, which will shorten the time needed to perform the analysis. However, all participants meeting analysis set criteria will be included in the final study report, regardless of the adaptive sample size target.

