**Table 6: Power and Sample Size Calculations**

Effect Size	Standard Deviation	80% Power	85% Power	90% Power
3.0	7.0	45	51	60
3.5	7.0	34	38	44
3.0	7.5	52	59	68
3.5	7.5	39	44	51
3.0	8.0	58	66	77
3.5	8.0	43	49	57

A preselected target sample size of 57 completers ( $n_0 = 57$ ) will provide 90% power to detect a difference of 3.5 points in means for the change from the baseline to the EOT Visit (after 6

weeks of treatment on XYWAV) in 24-hour average SBP when switching from twice-nightly high-sodium oxybate to XYWAV, assuming an SD of 8.0 points.

After 75% of participants have completed the study, an interim analysis will be conducted. If the study does not stop early for efficacy, conditional power for the primary endpoint will be calculated, and the adaptive sample size target may be increased up to a maximum of 77 participants (refer to Section [9.4](#)).

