### 3.5. Interim Analysis

The interim analysis will be performed after 43 participants (75%) have completed the study. Using the sample size assumptions described in Section 3.3, the calculated O'Brien-Fleming one-sided alpha levels for statistical significance are 0.00998 for the interim analysis and 0.02194 for the final analysis. If the primary endpoint is not rejected at the interim analysis, the final sample size will be adaptively determined based on conditional power.

Conditional power refers to the probability of reaching statistical significance at the final analysis given the data obtained at the interim analysis, and it is calculated according to equation (1):

$$CP = 1 - \Phi\left(\frac{z_{\alpha}\sqrt{n_2} - z_1\sqrt{n_1}}{\sqrt{\tilde{n}_2}} - \frac{z_1\sqrt{\tilde{n}_2}}{\sqrt{n_1}}\right) \quad (1)$$

Where:

$\Phi(\bullet)$  is the standard normal cumulative distribution function

$n_1$  = actual sample size at interim analysis (expected to be  $n_1 = 43$ )

$n_2$  = planned sample size at final analysis (i.e.,  $n_2 = 57$ )

$\tilde{n}_2$  = sample size increment between interim and planned final analyses (expected to be  $\tilde{n}_2 = 14$ )

$z_\alpha$  = the standard normal value for a type I error rate of  $\alpha$ ; i.e.  $\Phi(1-0.025)=1.95996$

$z_1 = \bar{x}_1 / se(\bar{x}_1)$ , the z-statistic for 24-hour SBP change from baseline computed at interim analysis

Given the conditional power, the final sample size target will then be determined using a "promising zone" approach:

- If  $CP \geq 90\%$  (Favorable zone): Continue enrolling more participants until prespecified target sample size ( $N = 57$ ).
- If  $CP < 40\%$  (Unfavorable zone): Continue enrolling more participants until prespecified target sample size ( $N = 57$ ).
- If  $40\% \leq CP < 90\%$  (Promising zone): Calculate additional sample size  $\tilde{n}'_2$  based on formula (2). The final sample size target will be adjusted to  $\min(77, n_1 + \tilde{n}'_2)$ .

$$\tilde{n}'_2 = \left( \frac{n_1}{z_1^2} \right) \left[ \frac{z_\alpha \sqrt{n_2} - z_1 \sqrt{n_1}}{\sqrt{n_2} - \sqrt{n_1}} + z_\beta \right]^2 \quad (2)$$

Where:

$n_1$  = actual sample size at interim analysis (expected to be  $n_1 = 43$ )

$n_2$  = planned sample size at final analysis (i.e.,  $n_2 = 57$ )

$z_\alpha$  = the standard normal value for a type I error rate of  $\alpha$ ; i.e.  $\Phi(1-0.025)=1.95996$

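### Protocol 9.4 adds the re-estimated increment to a literal 43 instead of the actual interim size n1, so its promising-zone target departs from SAP 3.5 whenever n1 is not 43 and the cap of 77 does not hide the difference

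*Protocol*

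**What the plan says.** Protocol 9.4 schedules the interim by a count: "An interim analysis will be performed after 43 participants (75%) have completed the study". In the conditional-power and increment formulas, however, n1 is the "actual sample size at interim analysis (expected to be" 43), so the formulas take whatever number is in the interim test. The planned final size n2 is 57 (Protocol 9.5: "A preselected target sample size of 57 completers").

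If conditional power is at least 40% and below 90%, Protocol 9.4 says to "increase the target sample size to" 43 plus the increment, "up to a maximum of 77 completers". The 43 is printed as a number.

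SAP 3.5 covers the same case differently: "The final sample size target will be adjusted to" min(77, n1 + increment), with n1 again the actual interim size.

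**The concern.** The increment is the number of further completers needed after the interim, and it is calculated from the actual n1. Adding it to a fixed 43 mixes two interim sizes. If n1 is above 43, n1 − 43 participants already observed are counted against the new recruits, and the trial comes out smaller than its own formula requires. If n1 is below 43, it comes out larger than required.

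The rule sets the final size of the primary confirmatory test, and the protocol and SAP state it differently. An adaptive rule should leave no choice between two targets once the interim result is known. In part of the promising zone the protocol version can also give fewer than 57 completers, which contradicts its own word for the action (increase) and the stated minimum of 57 in Protocol 9.5.

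**Working it through.** **Inputs.** Protocol 9.4: z_alpha = 1.95996, z_beta = 1.28155, n2 = 57, zone limits 40% and 90%, cap 77, interim one-sided alpha 0.00998 (z = 2.327). Protocol 9.5: difference 3.5, SD 8.0, one-sided 0.025. z1 is taken as positive for a fall in SBP. The actual n1 is not in the documents, so values other than 43 are assumptions.

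**The plan's own figures.** A one-sample t-test on the change (noncentral t) gives power 0.9008 at n = 57, and all 18 cells of Table 6 reproduce. O'Brien-Fleming levels at information fraction 0.75 come out at 0.00998 and 0.02194, as stated. 75% of 57 is 42.75, hence 43.

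**Formulas (Protocol 9.4).** Let B = (z_alpha·√n2 − z1·√n1)/√(n2 − n1). Then

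- CP = 1 − Φ(B − z1·√(n2 − n1)/√n1)
- increment = (n1/z1²)·(B + z_beta)²

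**Which base is right.** At CP = 90%, B + z_beta = z1·√(n2 − n1)/√n1, so the increment is exactly n2 − n1 = 57 − n1. Adding n1 returns 57, which joins the favorable zone without a jump. Adding 43 returns 100 − n1, which equals 57 only when n1 = 43. The two rules always differ by n1 − 43 before capping.

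**Examples (increment rounded up).**

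- n1 = 47, z1 = 2.1: B = (14.797 − 14.397)/3.162 = 0.127; increment = 10.658 × (0.127 + 1.28155)² = 21.1, so 22. CP is 80.0%. Protocol 43 + 22 = **65**; with n1, 47 + 22 = **69**.
- n1 = 49, z1 = 2.2: B = (14.797 − 15.400)/2.828 = −0.213; increment = 10.124 × (−0.213 + 1.28155)² = 11.6, so 12. CP is 86.5%. Protocol **55**; with n1, **61**.
- n1 = 42 at CP 80%: increment 27.7, so 28. Protocol **71**; with n1, **70**. Here the protocol over-sizes.

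**Targets by n1 (rounded up).**

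| n1 | CP 80%: protocol / with n1 | Just under CP 90%: protocol / with n1 | Protocol target below 57 from CP |
|---|---|---|---|
| 44 | 69 / 70 | 57 / 58 | never |
| 45 | 67 / 69 | 56 / 58 | 0.891 |
| 46 | 66 / 69 | 55 / 58 | 0.882 |
| 48 | 63 / 68 | 53 / 58 | 0.862 |
| 50 | 60 / 67 | 51 / 58 | 0.839 |

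The band is reachable: CP = 90% falls at z1 of about 2.26, below the stopping boundary of 2.327. Below CP of about 0.73 (n1 = 44) to 0.65 (n1 = 50) both rules reach 77 and agree.

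**Cost in conditional power.** At an interim CP of 80%, the intended 90% after re-estimation becomes 89.4% (n1 = 44), 88.1% (46), 86.4% (48) and 84.0% (50).

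**How often.** With z1 ~ N(δ·√n1/8, 1), δ from 2.0 to 3.5 mm Hg and n1 from 44 to 51, the targets differ in about 7–11% of trials. The protocol target is below 57 in 0% at n1 = 44, rising to at most about 4% at n1 = 51.

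**Caveat.** All figures use the protocol's increment. As read from the PDF, the increment formula in SAP 3.5 has √n2 − √n1 in the denominator where the protocol has √(n2 − n1). This may be an extraction artefact and should be checked against the original. Only the protocol form returns 57 − n1 at CP = 90%.

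**The case against.** The best defence is that the effect is nil at the planned n1 = 43 and that the SAP already has the rule right. Protocol section 9 describes itself as a summary and leaves technical detail to the SAP, and anyone who obtained a target below 57 from a rule worded as an increase would suspect a slip. This limits the practical risk. It does not remove the conflict: both documents define n1 as the actual count and then give different targets.

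Several stronger readings are tempting and do not stand:

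- *Enrollment continues during the interim, so n1 will exceed 43.* This does not follow. The trigger is a count of participants who have completed, and those enrolled during the analysis are treated as overruns. n1 could exceed 43 if the data cut is late, or if participants past the EOT Visit but not yet at the Safety Follow-up are included. It could fall below 43 if some of the 43 lack a valid recording for the Completer Set. The documents do not settle which.
- *The documents disagree whenever n1 is not 43.* They agree where both rules reach 77, and in the favorable and unfavorable zones, where the target is 57.
- *The target drops below 57 for every n1 above 43.* The value 100 − n1 is a limit at CP = 90%, which itself belongs to the favorable zone. In whole participants the drop starts at n1 = 45, in a narrow band.
- *Type I error is inflated.* The plan's justification speaks only of increases in sample size, so a decrease lies outside its wording. No inflation has been shown, and none is claimed here.

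**Conclusion.** The point holds as a drafting error in Protocol 9.4 that conflicts with SAP 3.5. With the cap not binding, the protocol target is wrong by n1 − 43 completers, in either direction. For the small departures from 43 considered here that is a few participants, and at an interim CP of 80% it costs up to 6 percentage points of conditional power (90% to 84.0% at n1 = 50). The frequencies of 7–11% (targets differ) and 0–4% (below 57) rest on SD 8 mm Hg, a true fall of 2.0 to 3.5 mm Hg, a normal z1 and an assumed n1 of 44 to 51. The documents give no actual n1, and at 43 there is no consequence. A reader might infer that the adaptive design as a whole is unsound; the documents do not support that, because the SAP version of the base is correct and the cap, zones and alpha levels are unaffected.

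**What to change.** In Protocol 9.4, replace 43 + increment with min(77, n1 + increment), and state that n1 is the number of participants actually in the interim test. This matches SAP 3.5, whose base needs no change. A separate floor of 57 is unnecessary, because n1 + increment already exceeds 57 at every conditional power below 90% in the promising zone. The cost is one line of protocol wording. The maximum of 77, the zone limits and the alpha levels stay as they are.

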## 9.5. Sample Size Determination

The sample size is dependent upon the results of the planned interim analysis (refer to Section 9.4). The sample size also accounts for a 60% screen failure rate after enrollment (ie, signing the ICF) during the Screening Period and assumes a 15% discontinuation/withdrawal rate during the Intervention Period. Based on these assumptions, approximately 170 (up to approximately 230) study participants will enroll to enable a minimum of 67 (up to approximately 91) to initiate the study intervention (ie, switch to XYWAV) and to capture complete data (both during the Screening Period and at the EOT Visit) for a minimum of 57 participants (up to approximately 77).

There are no historical data on 24-hour average BP changes in participants switching from twice-nightly high-sodium oxybate to XYWAV. Given the limited information, data from other studies with drugs similar to oxybate were leveraged to inform the design of this study. It was determined that an effect size of 3.0 or 3.5 with a SD range from 7.0 to 8.0 will be considered for power and sample size calculations. Sample sizes for different scenarios (different effect size and SD) were calculated ([Table 6](#)). Power calculations were performed assuming a 1-sided Type 1 error rate of 0.025.

**Table 6: Power and Sample Size Calculations**

Effect Size	Standard Deviation	80% Power	85% Power	90% Power
3.0	7.0	45	51	60
3.5	7.0	34	38	44
3.0	7.5	52	59	68
3.5	7.5	39	44	51
3.0	8.0	58	66	77
3.5	8.0	43	49	57

A preselected target sample size of 57 completers ( $n_0 = 57$ ) will provide 90% power to detect a difference of 3.5 points in means for the change from the baseline to the EOT Visit (after 6

weeks of treatment on XYWAV) in 24-hour average SBP when switching from twice-nightly high-sodium oxybate to XYWAV, assuming an SD of 8.0 points.

After 75% of participants have completed the study, an interim analysis will be conducted. If the study does not stop early for efficacy, conditional power for the primary endpoint will be calculated, and the adaptive sample size target may be increased up to a maximum of 77 participants (refer to Section [9.4](#)).

## **10. SUPPORTING DOCUMENTATION AND OPERATIONAL CONSIDERATIONS**

### **10.1. Regulatory, Ethical, and Study Oversight Considerations**

#### **10.1.1. Regulatory and Ethical Considerations**

- This study will be conducted in accordance with the protocol and with the following:
  - Consensus ethical principles derived from international guidelines including the Declaration of Helsinki and CIOMS International Ethical Guidelines
  - Applicable ICH GCP Guidelines
  - Applicable laws and regulations
- The protocol, protocol amendments, ICF, IB, and other relevant documents (eg, advertisements) must be submitted to an IRB/IEC by the investigator and reviewed and approved by the IRB/IEC and national regulatory authority (as applicable) before the study is initiated.
- Protocols and any amendments to the protocol will require IRB/IEC and national regulatory authority approval (as applicable) prior to initiation, except for changes necessary to eliminate an immediate hazard to study participants.
- The devices and systems involved in data collection for this study are in compliance with EMA/226170/2021.
- Decentralized aspects of this study, where applicable, are in compliance with local regulations, including the EU Recommendation Paper on Decentralized Elements in Clinical Trials - Version 01, 13 Dec 2022.
  - Site staff will train the participant on the use of the study devices, including how to report any AEs (serious and nonserious) that may occur during the study, at their first clinic visit, and the participant will be given additional reminders during the course of the study.
  - The participant will be provided with site and vendor 24-hour contact details for support with any safety or device issues that may arise.
- The investigator will be responsible for the following:
  - Providing written summaries of the status of the study to the IRB/IEC annually or more frequently in accordance with the requirements, policies, and procedures established by the IRB/IEC.
  - Notifying the IRB/IEC of SAEs or other significant safety findings as required by IRB/IEC procedures.
  - Providing oversight of the conduct of the study at the site and adherence to requirements of 21 CFR, ICH guidelines, the IRB/IEC, European regulation 536/2014 for clinical studies (if applicable), European Medical Device Regulation

2017/745 for clinical device research (if applicable), and all other applicable local regulations.

#### **10.1.2. Financial Disclosure**

Investigators and subinvestigators will provide the sponsor with sufficient accurate financial information as requested to allow the sponsor to submit complete and accurate financial certification or disclosure statements to the appropriate regulatory authorities. Investigators are responsible for providing information on financial interests during the course of the study and for 1 year after completion of the study.

#### **10.1.3. Informed Consent Process**

- The investigator or their representative will explain the nature of the study to the participant or their legally authorized representative and answer all questions regarding the study.
- Participants must be informed that their participation is voluntary. Participants or their legally authorized representative will be required to sign a statement of informed consent that meets the requirements of 21 CFR 50, local regulations, ICH guidelines, HIPAA requirements (where applicable), Regulation (EU) 2016/679 GDPR requirements (where applicable), and the IRB/IEC or study center.
- The medical record must include a statement that written informed consent was obtained before any study activities were performed, unless otherwise allowed by protocol criteria, and must also include the date the written consent was obtained. The authorized person obtaining the informed consent must also sign the ICF.
- Participants must be re-consented to the most current version of the ICF(s) during their participation in the study.
- A copy of the ICF(s) must be provided to the participant or their legally authorized representative.
- Participants who are rescreened are required to sign a new ICF.
- This hybrid study will allow participants to enroll either virtually or at a site. Local guidelines and regulations will be followed when using eConsent.

#### **10.1.4. Data Protection**

- Appropriate steps will be taken to protect participant's personal data according to HIPAA, GDPR, and other local regulatory requirements, where applicable.
- Participants will be assigned a unique identifier by the sponsor. Any participant records or datasets that are transferred to the sponsor will contain the identifier only; participant names will not be transferred.
- The participant must be informed that their personal study-related data will be used by the sponsor in accordance with local data protection law. The level of disclosure must also be explained to the participant, and the ICF must describe how their personal data will be used.

- The participant will be informed of data privacy regarding the use of electronic clinical outcome assessment devices in the ICF.
- The participant must be informed that their medical records may be examined by clinical quality assurance auditors or other authorized personnel or suppliers appointed by the sponsor, by appropriate IRB/IEC members, and by inspectors from regulatory authorities.
- The contract between the sponsor and study sites specifies the responsibilities of the parties' related data protection, including handling of data security breaches and respective communication and cooperation of the parties.
- Information technology systems used to collect, process, and store study-related data are secured by technical and organizational security measures designed to protect such data against accidental or unlawful loss, alteration, or unauthorized disclosure or access.

#### **10.1.5. Committee Structure**

A study-related steering committee (along with an associated charter) will be formed. This group will review and meet on an ad hoc basis to provide input on the protocol and significant study-related matters that arise and will assist with data interpretation at the conclusion of the study.

#### **10.1.6. Dissemination of Clinical Study Data**

As the sponsor of the study, Jazz Pharmaceuticals is solely responsible for disclosing results on ClinicalTrials.gov, EudraCT, and other public registries in accordance with applicable global laws and regulations. By signing this protocol, the investigator acknowledges that all posting requirements are solely the responsibility of the sponsor and agrees not to submit any information about the study or its results.

#### **10.1.7. Data Quality Assurance**

- All participant data relating to the study will be recorded on a printed CRF or eCRF unless transmitted to the sponsor or designee electronically (eg, laboratory data). The investigator is responsible for verifying that data entries are accurate and correct by physically or electronically signing the CRF.
- Guidance on completion of CRFs will be provided in CRF completion guidelines.
- The investigator must permit study-related monitoring, audits, IRB/IEC review, and regulatory agency inspections and provide direct access to source data documents.
- Monitoring details describing strategy (eg, risk-based initiatives in operations and quality such as risk management and mitigation strategies and analytical risk-based monitoring), methods, responsibilities, and requirements, including handling of noncompliance issues and monitoring techniques (central, remote, or on-site monitoring), are provided in the Monitoring Plan or contracts.

- The sponsor or designee is responsible for the data management of this study, including quality checking of the data.
- The sponsor assumes accountability for actions delegated to other individuals (eg, contract research organizations).
- Records and documents, including signed ICFs, pertaining to the conduct of this study must be retained by the investigator or institution/site as applicable, for the period of time established in the clinical study agreement entered into by the investigator's study site unless local regulations or institutional policies require a longer retention period. No records may be destroyed during the retention period without the written approval of the sponsor. No records may be transferred to another location or party without written notification to the sponsor.

